**Table 1: Study Assessments**

Timepoint (Study Day)	Screening	Treatment Period															Follow-Up	
	-14 to -1	0	1 (±1 hr)	2 (±2 hr)	5 p (±4 hr)	7 (±6 hr)	12 p (±6 hr)	14 (±6 hr)	19 p (±6 hr)	21 (±6 hr)	28 (±6 hr)	29 (±1 hr)	30 (±2 hr)	33 (±4 hr)	42 (±3 days)	56 (±5 days)	84 (±5 days)	112 (±5 days) or ET Visit
Informed Consent	X																	
Demographics/Medical History	X																	
Inclusion/Exclusion	X																	
Physical Examination a	X	X				X		X		X	X				X	X	X	X
Vital Signs b	X	X	X	X	X	X	X	X	X	X	X	X	X	X	X	X	X	X
Pulse Oximetry c		X				X		X		X	X							
Clinical Safety Labs d	X	X				X		X		X	X			X	X	X	X	X
Pregnancy test e	X	X														X		X
Hepatitis & HIV Screen	X																	
12-Lead ECG f	X	X					X				X					X		
Tetanus & VZV antibodies		X														X	X	X
PDAI Score		X				X		X		X	X			X	X	X	X	X
PK Sampling h		X	X	X	X					X	X	X	X	X				
Immunogenicity i		X						X		X	X					X	X	X
Study Drug Administration j		X				X		X		X	X							
Immunoglobulins (IgG, IgA, IgM) and IgG subtypes (IgG 1-4) k	X	X	X	X	X	X	X	X	X	X	X	X	X	X	X	X	X	X q
CIC		X			X	X	X	X	X	X	X			X	X	X	X	X
Anti-Dsg (1 & 3) antibody titer	X	X				X		X						X		X	X	X
C3 and AECA l		X						X						X		X	X	X
FCGR2A m by buccal swab		X																
RNAseq m		X						X						X		X	X	X
Urine IgG m		X						X						X		X	X	X
Immune phenotyping n		X								X						X		
Pemphigus immune response biomarkers		X			X	X	X	X	X	X	X			X	X	X	X	X
Optional Skin Biopsy		X	X	X				X						X		X	X	
Photography o		X												X		X	X	X
Adverse Events	To be collected from the date that the ICF is signed through the last study visit																	
Concomitant Medications	To be collected from within 14 days prior to Day 0 through the last study visit																	

ECG = electrocardiogram; ET= Early Termination; HIV = human immunodeficiency virus; ICF = informed consent form; PD = pharmacodynamic; PK = pharmacokinetic; VZV = varicella-zoster virus

- a: Complete **PE**, including weight, to be performed. Height and BMI will be additional assessments conducted at screening.

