### 5.2 Inclusion Criteria

A subject must meet the following criteria to be eligible for the study:

1. Willing and able to read, understand and sign an informed consent form;
2. Male or female  $\geq$  18 years of age;
3. Documented diagnosis of pemphigus vulgaris or foliaceus based on all 3 of the following criteria:
  - a. Documented clinical history consistent with pemphigus vulgaris or foliaceus (clinical presentation defined as mucosal and/ or skin lesions);
  - b. Presence of Anti-Dsg 1 or 3 antibodies above the upper limit of normal;
  - c. History of at least one positive tissue based test (biopsy, DIF)
4. Active disease: Lesions lasting  $>$  2 weeks, and 3 active lesions in skin or mucosa or 2 active lesions with at least one being a skin lesion  $>$  1 cm diameter:
  - a. If treated with rituximab or other anti-CD20 antibodies, last dose  $>$  12 months prior to screening;
  - b. If being treated with other immunosuppressants (i.e., azathioprine, mycophenolate mofetil or cyclosporine), must be on stable dose ( $<$  10% change in dose) for 6 weeks prior to screening;
  - c. If being treated with corticosteroids, must be  $\leq$  1mg/kg/day of prednisone or equivalent and stable ( $<$  10% change in dose) for 2 weeks prior to screening;

- d. Allowed topical therapies for pemphigus lesions upon entering the study include petroleum jelly or Aquaphor® for the skin or chlorhexidine for the mouth
5. Body mass index (BMI) 18.5 – 39.9 kg/m^2;
6. Has a negative pregnancy test (for women of childbearing potential) documented prior to the first dose of study drug;
7. Females of childbearing potential must agree to be abstinent or else use any two of the following medically acceptable forms of contraception (<1% per year failure rate) from the Screening Period through the final study visit: oral contraceptive, condom with or without spermicidal jelly, diaphragm or cervical cap with spermicidal jelly, or intra-uterine device (IUD). A female whose male partner has had a vasectomy must agree to use one additional form of medically acceptable contraception.
8. Females of non-childbearing potential, defined as surgically sterile (status post hysterectomy, bilateral oophorectomy, or bilateral tubal ligation) or post-menopausal for at least 12 months do not require contraception during the study.

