9. Males with female partners of childbearing potential, including males who are surgically sterile (post vasectomy), must agree to be abstinent or else use a medically acceptable form of contraception from the screening period through the final study visit.

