## 6 STUDY PROCEDURES

### 6.1 Informed Consent

All subjects must take part in the informed consent process. Adequate time must be allowed for the subject to ask questions and make a voluntary decision. No protocol-specific procedures, including screening procedures, are to be performed until the subject has signed and dated an IRB-approved ICF. Subjects may withdraw consent at any time. Participation in the study may be terminated at any time without the subject's consent as determined by the Investigator.

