### 7.18 Follow-up Day 112 (End-of-Study) or Early Termination Visit

On Day 112 ( $\pm$  5 days), subjects are to return to the clinic and the following procedures are to be performed:

- Complete physical exam ([Section 6.3](#))
- Vital sign measurements (after 5 minutes of rest; sitting blood pressure, heart rate, respiratory rate, oral temperature); abnormal results to be repeated after 5 minutes of rest ([Section 6.5](#))
- Clinical safety laboratory tests (hematology, serum chemistry panel, urinalysis) ([Section 6.7](#))
- Pregnancy test (Section 6.7)
- Serum tetanus antibody and VZV antibody testing if required. See [Section 6.7.3](#) for additional information.
- Immunogenicity sample collection (Section 6.7)
- PDAI Score ([Section 6.4](#))
- PD sample collection (Section 6.7)
  - IgG, IgG subtypes (IgG1-4), IgA, IgM
  - CIC
  - Anti-Dsg (1 and 3) antibody titer
  - C3
  - AECA
  - RNAseq
  - Urine IgG
  - Exploratory pemphigus immune response biomarkers
- Photography ([Section 6.11](#))
- Concomitant medication assessment ([Section 6.9](#))
- AE assessment ([Section 6.10](#))

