## 8 REMOVING SUBJECTS FROM STUDY

Every reasonable effort will be made to keep the subject in the study; however, if a subject is withdrawn from the study, every effort will be made by the Investigator to complete and report the reasons for withdrawal as thoroughly as possible. The reason(s) for termination must be clearly documented on the appropriate page of the eCRF. Once a subject discontinues from the study for any reason, every effort will be made to collect all clinical and laboratory data as scheduled for the Early Termination Visit (See [Table 1](#)). A termination eCRF must be completed for all enrolled subjects.

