### 8.1 Subject Withdrawal

A subject's participation in the study may be prematurely discontinued for any of the following reasons:

1. The subject wishes to withdraw from the study.
2. Request by a regulatory agency (e.g., Institutional Review Board).
3. Subject experiences a significant or intolerable AE.
4. The subject experiences a significant adverse change in vital signs, PE findings, or a clinical laboratory parameter.
5. The subject has a need for a concomitant medication that is not permitted by the study protocol.
6. The subject experiences generalized impairment or mental incompetence that would result in the subject being unable to understand his or her participation in the study.
7. If, in the Investigator's medical judgment, further participation would be injurious to the health and well-being of the subject, or is not in the best interest of the subject.
8. Administrative reasons, such as subject non-compliance or a major protocol violation.

Subjects who are withdrawn from this study due to an AE determined to be related to study drug are to be followed until there is either:

- Resolution or stabilization of the AE determined to be related
- The subject is lost to follow-up
- The event is otherwise explained

If there is a persistent AE contributing to discontinuation that is determined to be related to SYNT001, subjects must be followed with appropriate medical management until resolution or stabilization.

A reasonable effort should be made to contact any subject lost to follow-up during the study to complete assessments and retrieve any outstanding data. If the subjects are unreachable by telephone after three (3) attempts, the minimum of a registered letter should be sent requesting that contact be made with the Investigator to report survival information.

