**11.3.9.2 Time Frame for Reporting**

Any death, SAE or pregnancy experienced by the subject after informed consent through the last study visit, regardless of relationship to study drug, , must be promptly reported (within 24 hours of the Investigator becoming aware of the event) by telephone or electronic transmission to the sponsor (or designee).

Contact information for **SAE** reporting:

Medpace Clinical Safety  
Medpace SAE hotline:  
Telephone: PPD [redacted] dial P or PPD [redacted] dial P  
Facsimile: PPD [redacted] or PPD [redacted] D  
e-mail: PPD [redacted]

Additionally, the Investigator will be able to contact the **Medical Monitor**:

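### Contraception under inclusion criteria 7 and 9 ends at the final study visit with no minimum time after the last dose, so a subject who withdraws fully soon after an infusion may have 0 to 14 days of cover, against 84 for a completer

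*Protocol*

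**What the plan says.** Criterion 7 in Section 5.2 asks women of childbearing potential to use contraception "from the Screening Period through the final study visit". Under criterion 9, the rule for men whose partners could become pregnant is that they "must agree to be abstinent or else use a medically acceptable form of contraception from the screening period through the final study visit". The Synopsis repeats both. The term for the final visit is not defined, and neither criterion mentions the last dose.

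The last column of Table 1 is headed "112 (±5 days) or ET Visit", and Section 7.18 is titled "Follow-up Day 112 (End-of-Study) or Early Termination Visit". Day 112 and early termination therefore share one end-of-study slot.

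Complete withdrawal is foreseen. Section 6.1 states: "Subjects may withdraw consent at any time". The first reason listed in Section 8.1 is "The subject wishes to withdraw from the study". For anyone who discontinues, Section 8 says that "every effort will be made to collect all clinical and laboratory data as scheduled for the Early Termination Visit". That visit is not timed from the last infusion.

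The pregnancy reporting duty in Section 11.3.9.2 has the same end: "Any death, SAE or pregnancy experienced by the subject after informed consent through the last study visit".

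**The concern.** The length of contraception after exposure depends on when the subject leaves the study and not on when the subject was last dosed. A completer gets a long interval because the visit schedule happens to supply one. A subject who withdraws consent shortly after an infusion may get almost none.

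This is a safety rule for women of childbearing potential and for the partners of male subjects. The pregnancy test at the Early Termination visit covers only the time up to exit. Because pregnancy reporting also stops at the last visit, a pregnancy that begins soon after an early exit lies outside both the contraception duty and the 24-hour reporting duty as written.

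**Working it through.** **Inputs**

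- Dosing days: 0, 7, 14, 21 and 28 (Section 9.3), so the last planned dose is on Day 28.
- Later visits: Days 29, 30, 33, 42 (±3 days), 56 (±5), 84 (±5) and 112 (±5) (Table 1).
- Cover after the last dose = day of the final study visit - day of the last dose.

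**The plan's own figure.** The version 2.0 summary of changes describes Day 112 as 12 weeks after the last dose. Check: 112 - 28 = 84 days, and 84 / 7 = 12 weeks. With the visit window, 107 - 28 = 79 to 117 - 28 = 89 days. The figure is reproduced for a completer.

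**Five-dose subject who withdraws entirely, and cover added by a floor of 84 days after the last dose**

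| Last visit | Cover after the last dose (days) | With visit window | Added by the floor (days) |
|---|---|---|---|
| Day 28 | 28 - 28 = 0 | – | 84 - 0 = 84 |
| Day 29 | 29 - 28 = 1 | – | 84 - 1 = 83 |
| Day 42 | 42 - 28 = 14 | 11 to 17 | 84 - 14 = 70 |
| Day 56 | 56 - 28 = 28 | 23 to 33 | 84 - 28 = 56 |
| Day 84 | 84 - 28 = 56 | 51 to 61 | 84 - 56 = 28 |
| Day 111 (unscheduled) | 111 - 28 = 83 | – | 84 - 83 = 1 |

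A completer seen at the early end of the Day 112 window would gain 84 - 79 = 5 days. A subject who leaves on the day of any earlier infusion also has 0 days. The 14 is not a protocol limit. It marks exit by about Day 42, the clearly short range.

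**Scale.** The text that version 2.0 replaced set 30 days after the final dose for women and 60 for men. It is superseded, so departing from it is not an error, but it gives a yardstick. A last visit before Day 28 + 30 = 58 gives less than 30 days, and one before Day 28 + 60 = 88 gives less than 60. Section 9.6.2 expects IgG to return to within 30% of baseline within 4 weeks of dosing (for repeated doses, from primate data). An exit at 0 to 14 days falls inside that time.

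**Who is not affected.** Sections 5.1 and 8.3 keep subjects who miss doses in follow-up through all scheduled visits, and the individual stopping rule in Section 8.4.3 stops drug only. With a last dose on Day 21, such a subject has 112 - 21 = 91 days; with only the Day 0 dose, 112. Section 10 says that significant increases in anti-pemphigus medication lead to discontinuation from the study. That is not counted here as an exit route, because clarification letter 2.0 links the sentence to Section 8.4.3.

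**The case against.** The best counter-argument is that criteria 7 and 9 record what a subject agrees to at entry. At that moment the final visit is the scheduled Day 112 visit, and the version 2.0 summary says the contraception period was updated to run to Day 112. On that reading an early leaver has already agreed to contraception through Day 112, and the only defect is an undefined term. This reading is possible. But the criteria do not state it, and Table 1 and Section 7.18 treat early termination as the same end-of-study visit. The rule can be followed as written with 0 days of cover.

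Other points stand in part:

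- The documents shown give no half-life or reproductive-toxicity interval, so neither 0 to 14 days nor 84 days can be shown to be unsafe or sufficient.
- Only part of the file is shown and the consent pages were removed. They may carry a longer instruction.
- Zero days requires the infusion visit itself to be the last contact, and later exits give up to 83 days.
- The reporting gap is narrower than it first looks. Untoward events judged drug-related are still recorded when they become known after the reporting period (Section 6.10), and pregnancy complications count as adverse events (Section 11.2). An uncomplicated pregnancy is not caught.

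The follow-up rule for subjects who miss doses does not answer the point, since it cannot bind someone who has withdrawn consent.

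**Conclusion.** The concern holds, as a minor point with medium confidence. As written, the criteria guarantee no minimum cover after the last dose. The 84 days are secured only for subjects who stay to Day 112, and a five-dose subject who leaves fully between Day 28 and Day 42 has 0 to 14 days.

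This rests on reading the Early Termination visit as the final study visit for a subject who withdraws, and on no other part of the file setting a post-dose minimum. It concerns only complete withdrawals among subjects to whom criteria 7 or 9 apply, in a trial of about 16 and at most 27 subjects. No endpoint or dose decision changes.

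**What to change.** In criteria 7 and 9, in both Section 5.2 and the Synopsis, end contraception at the later of the final study visit and 12 weeks after the last dose of study drug received. The 12 weeks is the sponsor's own interval for Day 112; the sponsor should confirm it or replace it with one based on the drug's elimination and reproductive toxicology. Match the consent form, and have sites remind the subject at the Early Termination visit.

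The cost is one phrase in two criteria and the Synopsis, plus the consent wording. No visit or test is added. Early leavers carry the burden of longer contraception after exit, by the amounts in the table. Completers gain at most 5 days, and subjects who only stop dosing are unchanged. Use after exit cannot be verified, so the gain is a clear instruction and not enforcement.

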### **5.3 Exclusion Criteria**

A subject who meets any of the following criteria is ineligible for the study:

1. Unable or unwilling to comply with the protocol;
2. Active non-hematologic malignancy or history of non-hematologic malignancy in the 3 years prior to screening (exclusive of non-melanoma skin cancer and cervical cancer in situ);
3. Positive for HIV or hepatitis C antibody;
4. Positive for hepatitis B surface antigen;
5. Active infection or history of recurrent infections;
6. IVIG treatment within 60 days of screening;
7. Received any cytotoxic (other than azathioprine) or mAb therapy in the 3 months prior to screening;

8. Any exposure to an investigational drug or device within 30 days prior to screening;
9. Plasmapheresis or immunoadsorption within 60 days of screening
10. Cellular therapy, including CAR-T, at any time prior to screening
11. Use of any immunosuppressive drugs apart from corticosteroids, azathioprine, mycophenolate mofetil, or cyclosporine within 3 months of screening;
12. Serum total IgG < 600 mg/dL;
13. Subject has any current medical condition that, in the opinion of the Investigator, may compromise their safety or compliance, preclude successful conduct of the study, or interfere with interpretation of the results (e.g., a significant pre-existing illness or other major comorbidity that the Investigator considers may confound the interpretation of the study results);
14. Any vaccination within 2 weeks of screening

## 6 STUDY PROCEDURES

### 6.1 Informed Consent

All subjects must take part in the informed consent process. Adequate time must be allowed for the subject to ask questions and make a voluntary decision. No protocol-specific procedures, including screening procedures, are to be performed until the subject has signed and dated an IRB-approved ICF. Subjects may withdraw consent at any time. Participation in the study may be terminated at any time without the subject's consent as determined by the Investigator.

### 6.2 Demographics and Medical History

Demographics (age, gender, race and ethnicity) and medical history will be obtained from the subject and recorded on the source document and eCRF. Medical history will capture the subject's current medical history (current disease processes), past medical status (past disease processes), history of surgery and concomitant treatments, including relevant clinical response to past disease specific treatments and duration as well as dosing of such treatments.

### 6.3 Physical Examination

A complete physical examination will be performed as outlined in [Table 1](#). The complete PE will include measurements of weight (in kg) and height (in cm; height to be measured only at screening visit) and a review of the following body systems:

- General appearance
- Head, eyes, ears, nose, and throat
- Neck
- Respiratory
- Cardiovascular
- Abdomen
- Neurologic
- Extremities
- Dermatologic
- Lymphatic

Any abnormal and clinically significant findings from the PE must be recorded in the appropriate eCRF. Findings at screening and Day 0 (pre-dose) will be recorded as medical history.

### 6.4 Pemphigus Disease Area Index (PDAI) Scoring

Pemphigus severity and disease activity will be measured using the PDAI. See [Appendix B](#).

## 6.5 Vital Sign Measurements

Vital sign measurements will be collected after the subject has been sitting for 5 minutes. Vital sign assessments will include measurements of sitting blood pressure (mm Hg), heart rate (beats per minute), respiration rate (breaths per minute), oral temperature (Celsius). Abnormal results are to be repeated after 5 minutes of rest. Pulse oximetry (%) also is to be measured. See [Table 2](#) for timing window allowances with respect to measurement collection.

On Days 0, 7, 14, 21, and 28, vital sign measurements are to be obtained immediately prior to the infusion; 15, 30, and 45 minutes after the start of the infusion; at completion of the infusion; and 30 minutes, 1 hour and 2 hours following completion of the infusion. Details on the management of mild to moderate and severe infusion reactions can be found in [Figure 1](#) and [Figure 2](#). Abnormalities in vital sign measurements will be graded in severity per the NCI CTCAE scale Version 4.03.

Subjects should be seated quietly for at least 5 minutes in a chair with their backs supported, their feet flat on floor (legs uncrossed), and their arms bared on a hard surface, with the arm slightly abducted and bent, with palm up and the midpoint of upper arm at heart level. Correct cuff and bladder size should be utilized and the same cuff and arm should be used per subject throughout study.

## 6.6 12-Lead Electrocardiogram (ECG)

Digital 12-lead ECG measurements will be obtained at screening, on Days 0 and 28 at 5 minutes after the completion of the infusion and at the Day 56 visit. Subjects who conduct their Day 12 visit at the investigative site, as opposed to an at-home nurse visit, will have an additional ECG performed. ECGs are to be performed with the subject in a supine position having rested in this position for at least 5 minutes before each reading. ECGs are to be performed in triplicate, each 1 to 2 minutes apart. See [Table 2](#) for timing window allowances with respect to performing ECG.

The following ECG parameters will be collected: PR interval, QRS interval, and QT interval. The ECG findings will be evaluated by a qualified physician for the presence of abnormalities (qualitative assessment). The physician will assess each ECG as normal, abnormal/not clinically significant, or abnormal/clinically significant.

Normal QTcF is  $\leq 450$  msec.

Abnormalities in the ECG that appear following therapy or that result in clinical signs and symptoms are considered clinically significant for the purposes of this study and will be recorded on the AE eCRF.

### 6.7 Clinical Laboratory Measurements

Collection time for all safety, PD, and exploratory labs are outlined in [Table 1](#).

Laboratory testing (hematology, urinalysis, serum chemistry, virology, serology, pregnancy tests, PD samples, PK samples, and anti-drug antibody samples) will be performed using established methods by a central laboratory. Safety laboratory panels are defined as listed in Table 3. Blood and urine samples for hematology, serum chemistry, and urinalysis will be prepared using standard procedures. Results will be provided to the Investigator. Aliquots from the PK, biomarker and anti-drug antibody samples may be retained as back-up for additional testing as necessary. Subjects will be in a seated or supine position during blood collection. Full clinical safety lab draws will be collected at Screening and on Days 0, 7, 14, 21, 28, 33, 42, 56, 84 and 112. The total blood draw for each subject who completes the study at Day 112, will be approximately 433 mL. Please refer to the Laboratory Manual for more information.

